## 5. TREATMENT PLAN

Treatment will be administered on an outpatient basis. Lenalidomide 2.5 mg, 5 mg, 10 mg, 15 mg and 25 mg capsules are to be taken orally (PO). In Phase I, the starting dose of Lenalidomide is 10 mg taken PO daily for 3 consecutive weeks (Days 1-21) following one week off therapy (Days 22-28). One cycle is 4 weeks (Figure 1).

**Figure 1:** Phase 1 and Phase 2 Lenalidomide Dosing Schema

In phase 1, it is anticipated that 6 - 18 evaluable patients will be treated. Three to six patients will be treated at each dose level of three dose levels of Lenalidomide (10 mg, 15 mg, 25 mg) daily doses (Table 1). The initial dose is 10 mg. Patients will receive repeated cycles of Lenalidomide until disease progression or unacceptable toxicity. If no Lenalidomide related Dose Limited Toxicity (DLT) is seen in three patients at a dose level during first cycle (by day 28), the escalation to the next dose level is allowed. Each cohort will be monitored for a DLT during the first cycle before deciding to escalate the dose for the next cohort.

**Table 1:** Phase 1 Dose ranging

Dose Level	Daily Dose (once a day)	Number of Patients	Escalation Rule *
-1	5 mg	3 – 6	If 0/3 DLT or 1/3 DLT add 3 patients
1 (Starting Dose)	10 mg	3 – 6	If 0/3 DLT escalate 1/3 DLT add 3 patients
2	15 mg	3 – 6	If 0/3 DLT escalate 1/3 DLT add 3 patients
3	25 mg	3 – 6	If 0/3 DLT or 1/3 DLT add 3 patients

\* Dose escalation rules are described in details in Table 2.

Dose escalation determination is summarized in Table 2. If one DLT occurs at a dose level, up to 3 additional patients will be added to that cohort and if one or more of this group suffers DLT, then dose escalation is stopped, and this dose is declared the Maximally Tolerated Dose (MTD). Three additional patients will be entered at the next lower dose level if only three patients were treated previously at that dose.

**Table 2:** Determination of Lenalidomide Capsules Maximum Tolerated Dose (MTD)

Number of Patients with DLT at Given Dose Level	Dose Escalation Rule
0 out of 3	Enter three patients at the next dose level
≥ 2	Dose escalation will be stopped. This dose level will be declared MTD. Three additional patients will be recruited at the next lower dose level if only three patients were treated previously at that dose.

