1 out of 3	Recruit at least three more patients at this dose level. 
 
• If none of these patients experience with DLT, proceed to the next higher dose level
 
• If one or more of this group suffer DLT, then dose escalation is stopped and this dose is declared MTD. Three additional patients will be entered at the next lower dose level if only three patients were treated previously at that dose.
 

≤ 1 out of 6 at highest dose level below the MTD	This will be the recommended Phase 2 dose. At least six patients must be recruited at the recommended Phase 2 dose.

If no DLT is observed at the final 25 mg dose level in the first three patients, three additional patients at the 25 mg dose level will be recruited. In Phase 1, in order to declare Therapeutic Dose Level (TDL), a minimum of six patients must be recruited at that dose level. Therapeutic

Dose Level (TDL) is defined as the dose level where DLT occurred in less or equal to one out of six patients below the Maximally Tolerated Dose level. TDL will be the recommended dose for Phase 2.

If a DLT is observed in two or more patients at the first dose level (10 mg), then dose level -1 (5 mg) will be tested with three patients first. Three additional patients will be enrolled at the 5 mg dose, if one or less DLT is observed. If one or more of this group suffers DLT, then the study is stopped and lenalidomide maintenance for elderly AML patients post autologous transplant is not deemed feasible (same as if  $\geq 2$  had a DLT to initial cohort of 5 mg).

Decisions about DLTs, expansion of a cohort to six subjects, escalation to the next dose level, or reduction to the next lower level will be made by Principle Investigator.

In Phase 1, subjects will continue study drug, lenalidomide until disease progression or unacceptable toxicity. Reported adverse events and potential risks for lenalidomide are described in Section 2.5. Dose modifications are described in Sections 5.1 and in Table 3. Subjects who are withdrawn without a DLT before completing Cycle 1 will not be used to evaluate the MTD or TDL, but will be included in the overall safety analysis.

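### At 5 mg, one DLT in six patients stops the trial if it falls in the second three but not in the first three, although the plan elsewhere accepts one in six

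*Combined protocol and SAP*

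**What the plan says.** All of this is in Section 5 (Treatment Plan).

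- **Opening 5 mg.** The condition is "If a DLT is observed in two or more patients at the first dose level (10 mg), then dose level -1 (5 mg", and three patients are treated there first. Table 2 says of a level with two or more DLTs: "Dose escalation will be stopped. This dose level will be declared MTD". So 10 mg is then the MTD, and 5 mg lies below it.
- **Expansion at 5 mg.** "Three additional patients will be enrolled at the 5 mg dose, if one or less DLT is observed". Table 1 agrees for level -1: "If 0/3 DLT or 1/3 DLT add 3 patients".
- **Stop at 5 mg.** The next sentence reads "If one or more of this group suffers DLT, then the study is stopped", and the treatment "is not deemed feasible (same as if" two or more of the initial 5 mg cohort had a DLT).
- **Acceptable dose.** The TDL, which becomes the Phase 2 dose, is the level where "DLT occurred in less or equal to one out of six patients below the Maximally Tolerated Dose level". The last row of Table 2 uses the same limit. Neither sets a condition on the order of events.
- **General rule for an added cohort.** "If one DLT occurs at a dose level, up to 3 additional patients will be added to that cohort"; escalation ends if one or more of those added has a DLT.

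**The concern.** In the general rule, the added three are judged only after a DLT has already occurred, so one more makes at least two in six. At 5 mg, almost the same wording also covers patients added after 0/3, where one DLT makes only one in six. The plan calls that result acceptable in its TDL definition and in Table 2, yet here it closes the study.

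The two possible outcomes are far apart. One ends the trial with a clinical conclusion that lenalidomide maintenance is not feasible in these patients. The other sends 30 patients into Phase 2 at 5 mg. With one DLT in six, the choice between them depends only on whether the affected patient was among the first three or the last three.

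**Working it through.** **Inputs.** The decision rules come from Section 5 and its Tables 1 and 2. The documents state no DLT rate and no operating characteristics for Phase 1, so there is no figure of the plan's own to reproduce. The rates below are assumptions. Write p for the DLT rate and q = 1 − p.

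**Step 1. Compare outcomes with one DLT in six.**

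| Dose and sequence | Total | Result under Section 5 |
|---|---|---|
| 5 mg: 1/3, then 0/3 | 1/6 | No stop applies; meets the TDL definition |
| 5 mg: 0/3, then 1/3 | 1/6 | Study stopped, not feasible |
| 10 mg: 0/3, then 1/3 when filled to six after 15 mg is declared the MTD | 1/6 | Recommended Phase 2 dose |

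Of the 64 possible DLT sequences in six patients, the written 5 mg rule and the one-in-six limit disagree on exactly three: the single DLT in patient 4, 5 or 6.

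**Step 2. Probability of each order once 5 mg is open.**

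- P(0/3 then 1/3) = q³ × 3pq² = 3pq⁵
- P(1/3 then 0/3) = 3pq² × q³ = 3pq⁵

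The two are equal for every p, so given exactly one DLT in six the written rule stops half of trials. The disputed path, 3pq⁵, is 11.6%, 17.7%, 20.0%, 19.7%, 17.8% and 15.1% at p = 5%, 10%, 15%, 20%, 25% and 30%.

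**Step 3. Chance of continuing, given that 5 mg is open.**

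| Rule | Formula | p = 10% | 20% | 30% |
|---|---|---|---|---|
| Stop at any DLT in six | q⁶ | 53% | 26% | 12% |
| As written | q⁶ + 3pq⁵ | 71% | 46% | 27% |
| Stop at two or more in six | q⁶ + 6pq⁵ | 89% | 66% | 42% |

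The written rule is the average of the two order-free rules.

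**Step 4. Share of all trials.** 10 mg passes escalation with 0/3, or with 1/3 then 0/3, so P(10 mg fails) = 1 − (q³ + 3pq⁵). Multiply by the 5 mg path from Step 2.

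| Rate at 10 mg | Rate at 5 mg | P(10 mg fails) | 3pq⁵ at 5 mg | Share of trials |
|---|---|---|---|---|
| 5% | 5% | 0.027 | 0.116 | 0.3% |
| 10% | 10% | 0.094 | 0.177 | 1.7% |
| 20% | 20% | 0.291 | 0.197 | 5.7% |
| 30% | 30% | 0.506 | 0.151 | 7.7% |
| 20% | 10% | 0.291 | 0.177 | 5.2% |
| 30% | 10% | 0.506 | 0.177 | 9.0% |
| 30% | 20% | 0.506 | 0.197 | 9.9% |

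Also counting failure of 10 mg when it is later filled to six adds at most 0.6 percentage points at flat rates of 10% to 30%.

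**The case against.** **It is a rarely used fallback.** 5 mg is not one of the three planned levels. It opens only if 10 mg fails, and Section 2.4 chose 10 mg for its tolerability after transplant in myeloma. This stands and limits the severity: at a flat 5% rate the share is about 0.3% of trials.

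**The error is conservative, and there is oversight.** The rule stops early; it exposes nobody to a worse dose and does not bias the Phase 2 estimate. The monitoring committee reviews adverse events monthly and advises on continuation (Section 11.1). The first part stands. The second does not override a written stop.

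**The sponsor may want a DLT-free confirmation cohort.** The 5 mg paragraph never says that 1/3 then 0/3 passes; that follows from the absence of a stop and from the TDL definition. A deliberate requirement of this kind is possible. But no reason is given, general caution at the lowest dose would also stop 1/3 then 0/3, and the TDL definition would still need an exception for 5 mg.

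**The stop might refer to all six patients.** This reading fails. Any DLT in the first three would then stop the study, so adding patients after 1/3 would be pointless and the parenthesis about two or more in the initial cohort would make no sense.

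A reader might also infer that staff would not know what to do, or that the same fault runs through the general rule. The documents support neither. The specific 5 mg stop governs conduct, and the general rule applies its wording only after a first DLT.

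**Conclusion.** The concern holds. A result of 0/3 then 1/3 at 5 mg closes the trial although it meets the plan's own standard for an acceptable dose, while the same count in the other order does not close it. The even split given one DLT in six needs only independent DLTs with a common rate at 5 mg.

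How often it matters depends on assumed rates: about 0.3% to 7.7% of all trials at flat rates of 5% to 30%, up to about 9.9% among the scenarios where 5 mg is less toxic than 10 mg, and 12% to 20% once 5 mg is open. Severity is minor to moderate: the consequence is large, but the path is contingent and the direction conservative.

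It would go too far to call this a safety hazard, or to say that no safety aim could explain the rule. What the documents show is an inconsistency with the TDL definition and Table 2, with no stated rationale.

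**What to change.** Replace the stopping sentence for 5 mg with:

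> *If two or more patients treated at 5 mg have a DLT at any time, whether in the first three or among all six, the study stops and lenalidomide maintenance in this population is declared not feasible. If at most one of six has a DLT, 5 mg is the TDL.*

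The words about the first three must stay. The present parenthesis is the only explicit stop for two or more DLTs in the initial 5 mg cohort, and Table 2's row for that result points to a next lower dose, which does not exist below 5 mg. The infeasibility conclusion must also stay, since it appears nowhere else.

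**Cost.** One sentence, and no extra Phase 1 patients, because all six have been treated when the decision changes. It does loosen a safety stop: once 5 mg is open, the chance of continuing rises from 71% to 89%, 46% to 66% and 27% to 42% at true rates of 10%, 20% and 30%. In the trials where the decision changes, 30 Phase 2 patients would be enrolled at 5 mg who otherwise would not be.

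**Stricter alternative.** If the sponsor prefers to stop at any DLT among the six, that also removes the dependence on order, with chances of continuing of 53%, 26% and 12%. It needs more edits: remove expansion after 1/3 from the text and from Table 1 for level -1, set the TDL criterion at 5 mg to 0/6, and exempt 5 mg from the last row of Table 2.

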### **5.1 Dose modifications**

At Phase 1, subjects who develop any DLT during cycle 1 will be taken off the study. During cycle 2 and onward, dose reductions are allowed. Dose reduction rules are the same for subjects enrolled in Phase 2 (Table 3). Reduced doses will not be re-escalated for any subject during the study. Subjects may not continue Lenalidomide after the third dose reduction or beyond dose of 2.5 mg.

**Table 3: Lenalidomide Capsules Dose Modifications**

Original Daily Dose (mg)	First Dose Reduction (mg)	Second Dose Reduction* (mg)	Third Dose Reduction* (mg)
5	2.5	Discontinue	N/A
10	5	2.5	Discontinue
15	10	5	2.5
25	15	10	5

\* Subjects may not continue Lenalidomide after third dose reduction or beyond dose of 2.5 mg.

A non-hematologic DLT is defined as a National Cancer Institute (NCI)-Common Terminology Criteria for Adverse Events (CTCAE) Version 4 (Oct/09) Grade 3 or 4 adverse events (AE) considered related to the study drug. Grade 3 anorexia and Grade 3 fatigue are excluded since it is very common to develop anorexia and fatigue during any chemotherapy.

A hematologic DLT is defined as a grade 4 hematologic toxicity complicated by infection, severe hemorrhage, or marrow aplasia persisting greater than 2 weeks considered related to the study drug.

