### **Life-threatening**

Any adverse drug experience that places the patient or subject, in the view of the investigator, at immediate risk of death from the reaction as it occurred. It does not include a reaction that, had it occurred in a more severe form, might have caused death.

Adverse events (AEs) will use the descriptions and grading scales found in the revised

Common Terminology Criteria for Adverse Events (CTCAE) version 4.0.

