### 9.5 Expedited reporting

This section outlines adverse events that require expedited reporting.

The following be reported as a SAE:

- **Grade 2 (moderate) and Grade 3 (severe) Events** – Only events that are Unexpected and Possibly, Probably or Definitely Related/Associated with lenalidomide.
- **ALL Grade 4 (life threatening or disabling) Events** – Unless expected AND specifically listed in protocol as not requiring reporting (see section 9.8).
- **ALL Grade 5 (fatal) Events** – When participant is enrolled and actively participating in the trial OR when event occurs within 30 days of the last study intervention.

MEDWATCH 3500A form will be used to report SAEs to Montefiore Medical Coordinating Center and to Celgene Corporation for this study.

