#### Expedited AE reporting timelines:

**24 Hours; 5 calendar days** – The investigator must initially report the AE within 24 hours of learning of the event followed by a completed AE report within 5 calendar days of the initial 24-hour report.

**10 calendar days** – A complete AE report on the AE must be submitted within ten calendar days of the investigator learning of the event. Any medical event equivalent to CTCAE grade 3, 4, or 5 that precipitates **hospitalization (or prolongation of existing hospitalization)** must be reported regardless of attribution and designation as expected or unexpected with the exception of any events identified as protocol specific expedited adverse event reporting exclusions (Section 9.8)

Hospitalizations are defined as lasting 24 hours or longer and these events must be reported via an expedited manner.

Any event that results in persistent or significant disability/incapacity, congenital anomaly, or birth defect must be reported via an expedited AE mechanism.

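### The DLT definitions stop at grade 4, so a related cycle 1 death recorded only as grade 5 is not a DLT as written

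*Combined protocol and SAP*

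**What the plan says.** The two DLT definitions stand in section 5.1, below Table 3. A non-hematologic DLT is one of the CTCAE version 4 "Grade 3 or 4 adverse events (AE) considered related to the study drug"; grade 3 anorexia and grade 3 fatigue are the only exceptions. A hematologic DLT is a related grade 4 toxicity with infection, severe hemorrhage or prolonged marrow aplasia. Neither definition mentions grade 5 or death.

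Section 5 builds the escalation rule on that count. The trigger reads "If no Lenalidomide related Dose Limited Toxicity (DLT) is seen in three patients at a dose level during first cycle (by day 28"), and the next level is then allowed. One DLT in three requires three more patients. On evaluability the section says: "Subjects who are withdrawn without a DLT before completing Cycle 1 will not be used to evaluate the MTD or TDL".

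Elsewhere grade 5 is a grade of its own. Section 9.5 lists "ALL Grade 5 (fatal) Events" apart from grade 4, which it labels life threatening or disabling. Its timelines paragraph spells out all three grades when all three are meant: "Any medical event equivalent to CTCAE grade 3, 4, or 5 that precipitates" hospitalization.

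**The concern.** The most severe toxicity appears to be the one the counting rule leaves out. A related grade 3 event in cycle 1 counts toward stopping escalation; a related death recorded only as grade 5 does not. The DLT count sets both the escalation path and the Phase 2 dose, which 30 further patients are to receive.

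Such a death is possible. Section 2.5 says side effects can be fatal and lists heart attack, cardiopulmonary arrest and stroke. Patients are aged 60 to 80 and are screened within 100 days of transplant.

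**Working it through.** **1. Does any text bring grade 5 in?** The non-hematologic definition names grades 3 and 4. The hematologic definition names grade 4. Section 5 and Tables 1 and 2 refer to DLTs without redefining them. Section 5.1.2 uses open-ended thresholds (grade 3 and above for neurologic toxicity, grade 2 and above for cardiac toxicity), but those govern dose modification after cycle 1 in Phase 1, not DLTs. Grade 5 appears only in the reporting rules of section 9.5. So no text does.

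**2. Which deaths are affected?** Only related cycle 1 deaths with no related grade 3 or 4 non-hematologic event recorded on the way (other than the excepted grade 3 anorexia or fatigue) and no qualifying grade 4 hematologic toxicity.

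**3. How would such a patient be handled?** The text does not settle it.
- *Outside the evaluation.* The patient is treated as withdrawn without a DLT and drops out of the MTD and TDL assessment. Replacement is an inference, because section 5 does not state it. Death is also not listed among the removal criteria in section 5.4.
- *Kept as a non-DLT.* This is less natural, since the patient did not complete the cycle, but a count of 0/3 would then allow escalation.

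**4. Illustrative size.** The plan states no figure to reproduce. The inputs are assumptions: T, the total cycle 1 DLT risk with deaths counted (25% or 33%), and f, the part of T that is fatal and missed by the definition (0.1, 0.5 or 1 percentage point). The formula applies to 10 and 15 mg only, because 5 and 25 mg follow other rules.

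P(pass) = (1−p)³ + 3p(1−p)² × (1−p)³

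- Deaths counted: p = T
- Patient dropped and replaced: p = (T−f)/(1−f)
- Patient kept as a non-DLT: p = T−f

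For T = 0.25 with deaths counted: 0.4219 + 0.1780 = 0.5999.

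| T | f | Counted | Replaced | Kept |
|---|---|---|---|---|
| 25% | 0.1 | 60.0% | 60.1% | 60.2% |
| 25% | 0.5 | 60.0% | 60.8% | 61.1% |
| 25% | 1.0 | 60.0% | 61.6% | 62.2% |
| 33% | 0.1 | 43.4% | 43.6% | 43.6% |
| 33% | 0.5 | 43.4% | 44.1% | 44.4% |
| 33% | 1.0 | 43.4% | 44.8% | 45.4% |

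**5. When it would matter.** The probability of exactly one such death in the first three patients, with the other two DLT-free, is 3f(1−T)². At T = 0.25 this is 3 × 0.001 × 0.5625 = 0.17% to 3 × 0.01 × 0.5625 = 1.69% per level. In that event:
- If the death counts, three more patients are needed and all must be DLT-free: 0.75³ = 42.2% chance of passing.
- If the patient is replaced, with r = (T−f)/(1−f), the chance is (1−r) + r(1−r)³ = 85.6–86.3%.
- If the patient is kept, the level is passed at once.

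**6. Over the whole of Phase 1.** Section 5 says "it is anticipated that 6 - 18 evaluable patients will be treated". The chance of at least one such death is 1−(1−f)ⁿ: 0.6–5.9% for n = 6 and 1.8–16.5% for n = 18. The last figure pairs the largest assumed f with the maximum number of patients.

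**The case against.** The strongest objection is that the gap is almost empty and already guarded.

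- Section 9.1 defines a life-threatening event as one putting the patient "at immediate risk of death from the reaction as it occurred", and section 9.5 equates life threatening with grade 4. Most fatal reactions pass through that state, and if it is recorded the event is already a DLT. Fatal infection or hemorrhage with a related grade 4 cytopenia is caught by the hematologic definition.
- Judgement is built into the rule. Section 5 assigns "Decisions about DLTs, expansion of a cohort to six subjects, escalation to the next dose level" to the principal investigator, and escalation after 0/3 is permitted, not required.
- Fatal events on study are reported as SAEs. The DSMC reviews adverse events monthly and makes recommendations on continuation (section 11.1).

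All of this stands, and it limits the weight of the point. It does not change the counting rule: these safeguards depend on someone choosing to override the written definition.

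A reader might infer three stronger things that the documents do not support:
- *That a drug-related death would let escalation proceed unnoticed.* The investigator's role, SAE reporting and DSMC review make that unlikely.
- *That the protocol directs such a patient to be replaced.* It does not say so.
- *That the uncaptured fatal risk is capped at 1%, from the uncommon side effects in section 2.5.* The same section puts clots in the lungs, heart or brain, abnormal heart beats and pneumonia at 1–10%. All these rates are for events of any severity and are not limited to cycle 1, so they bound the fatal rate in neither direction.

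**Conclusion.** The point holds as a wording error in a safety rule: followed literally, section 5.1 does not count a related cycle 1 death recorded only as grade 5. The probability is low and the intended meaning is hardly in doubt.

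On average the effect is small: about 0.2 to 2.2 percentage points on the chance of passing a level at an assumed 25% DLT risk, and 0.1 to 2.0 points at 33%. These figures rest wholly on assumed rates and on two readings that the text leaves open. A larger assumed fatal rate would give a larger shift, but the documents give no basis for choosing one.

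The case for correction rests on the individual event. If one such death occurs among the first three patients and the other two are DLT-free, the rule as surely intended requires three more patients at that level, and the literal rule does not.

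**What to change.** In section 5.1, change the opening of the phrase "Grade 3 or 4 adverse events (AE) considered related to the study drug" so that it reads *Grade 3 or higher*, leaving the rest of the phrase and the grade 3 anorexia and fatigue exceptions as they are. Then add: *Any death in cycle 1 considered related to the study drug, hematologic or not, is a DLT.*

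The added sentence is needed because a death coded under a hematologic term would not be reached by the amended non-hematologic definition. A further clause keeping such patients evaluable for the MTD and TDL is optional: section 5 excludes only subjects withdrawn without a DLT, so a death that counts as a DLT already stays in.

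The cost is one changed phrase and one new sentence.
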